## **DATA COLLECTION**

All data collection will occur via secure digital link to online surveys that will be linked by unique, anonymized participant identification numbers. Data collection, via this process will occur in the (1) screener, (2) pre-randomization, pre-intervention or control data collection, (3) post- data

collection, (4) 3 months post-data collection, and (5) 6 months post data collection, Please see the trial's schema below.

## SCHEMA, RANDOMIZED CONTROLLED PILOT TRIAL

[figure not shown]
## STATISTICAL POWER

As a pilot study, this project is not statistically powered.

## STATISTICAL ANALYSIS PLAN

Descriptive statistics will be used to identify the characteristics of the sample. Baseline differences between the intervention group and control group will be examined using student's t tests (for continuous variables) or chi-square tests (for categorical variables). Second, the feasibility / acceptability / satisfaction will be evaluation through multiple indicators, with focus on the simple question, "I like this app."

Preliminary efficacy of the intervention will be assessed using both bivariate statistics (e.g., t test, chi-square test, and fisher exact test) and multivariate statistics adjusting for demographic factors and baseline differences. To examine the preliminary effect of the intervention, we compared changes over time in HIV knowledge, pre-exposure prophylaxis knowledge, internalized homophobia, everyday discrimination, and medical mistrust within each group, as well as the increase from baseline to 6-month between the two groups. We also will assess the differences in willingness to take HIV test, self-reported HIV testing rates, and interest in learning more about pre-exposure prophylaxis and pre-exposure prophylaxis consultation with prescription between the two groups using Chi-square and Fisher's exact test. The effect of the intervention will be further examined using a generalized estimating equation controlling for potential confounders including education, income and social support. All statistical analyses will be performed using the SAS 9.4 statistical software package.

Institutional Review Board  
**Protocol Oversight Review Form**Date Submitted to IRB: August 15, 2018Title of Project: Adapting and Pilot Testing a Behavioral Intervention to Incorporate Advances in HIV Prevention for Black Young MSM in AlabamaName of Principal Investigator: [name]

Signature of Principal Investigator: \_\_\_\_\_

School: Public HealthDepartment: Health Care Organization and PolicyDivision: NA

Review Process (as determined by Department Chair):

Departmental Review  
 Divisional Review (Division Director or Designate)  
 Center or Departmental Protocol Review Committee Review  
 Project Review Panel (PRP)—Appointed by the Department Chairman or Division Director (PRP report attached)

[figure not shown]
---

I have reviewed the proposed research and concluded that the following apply:

- The research is scientifically valid and is likely to answer the scientific question;

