## **PROTOCOL**

The purpose of this study is to adapt and test Brothers Saving Brothers, a brief two-part intervention that has been shown to increase rates of HIV testing and acceptance of prevention education in Midwest Black young men who have sex with men but has not been adapted for the South. This will be accomplished by updating it for rapid testing, pre-exposure prophylaxis education, and to include structural supports. We will pilot-test the adapted intervention to estimate intervention effects.

Community Based Organization staff will facilitate the enrollment process. Potential participants will directly enter data into a virtual screener via Qualtrics. Data will be directly uploaded and stored on a secure, encrypted server. Inclusion criteria include age, identifying as Black, English speaking, resident of Alabama, being sexually active with men, identifying as male, and has not taken an HIV test in the prior 6 months. If eligible, the participant will be asked to provide informed consent. Informed consent will include the request to access medical records related to HIV re-testing and pre-exposure prophylaxis. Limited data on rates of pre-exposure prophylaxis exist, but since this study is with high-risk for HIV young men who have sex with men, we anticipate most participants will be eligible for pre-exposure prophylaxis per guidelines. After informed consent is collected, pre-study survey data will be self-reported. The system will then randomize participants to Kings or the standard control condition in a 2:1 allocation. Participants will be followed by 6-months post-enrollment.

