## **SAMPLE SIZE**

The original target sample size was N=60; however, this study ultimately enrolled N=59.

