**b. Describe how outcomes will be measured for this protocol.** Community Based Organization (CBO) staff will facilitate the enrollment process. Potential participants will directly enter data into an iPad screener (via the iSurvey platform). For more information of the iSurvey platform, please visit <https://www.harvestyourdata.com/>. Data will be directly uploaded and stored on a secure, encrypted UAB server, that will be established through UAB Central IT with the assistance of the UAB School of Public Health IT team. The device will determine eligibility. Inclusion criteria include age, identifying as Black, English speaking, resident of AL, being sexually active with men, identifying as male (will include YTGW and those transitioning depending on Aim 1 results), and has not taken an HIV test in the prior 6-months. If eligible, the participant will be asked to provide informed consent. Informed consent will be written and require a physical signature. Informed consent will include the request to access medical records related to HIV re-testing and PrEP uptake. Limited data on rates of PrEP eligibility exist, but since this study is with high-risk for HIV YMSM, we anticipate most participants will be eligible for PrEP per guidelines. After informed consent is collected, pre-study survey data (see Table with tentative variables below; a full survey will be included via amendment in 2020, about 1 year before I begin to collect data from study participants) will be self-reported (the participant will enter his own responses on the device further ensuring confidentiality) on the same device. The system will then randomize participants to aBSB (N=30) or control (N=30). Block randomization will ensure a balance across intervention and control groups. Data collection will occur for 18 months: 12-months of recruitment followed by 6-months of follow-up.

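### Part of the covariate set for the adjusted efficacy models appears to depend on baseline significance tests; a short fixed list, with the outcome's own baseline value for the continuous scales, would serve better

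*Combined protocol and SAP*

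**What the plan says.** The Statistical Analysis Plan section opens with a comparison of the arms at baseline: "Baseline differences between the intervention group and control group will be examined using student's t tests", with chi-square tests for categorical variables. Its next paragraph says that preliminary efficacy will be assessed with bivariate statistics and with "multivariate statistics adjusting for demographic factors and baseline differences". The demographic factors are not itemised. No alpha, candidate list or rule says when a baseline difference leads to adjustment.

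Later in the same paragraph the intervention effect is examined further with a "generalized estimating equation controlling for potential confounders including education, income and social support". Those three covariates do not depend on any baseline test, although the word introducing them leaves the list open.

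The Protocol section places the self-reported pre-study survey before allocation and then states: "The system will then randomize participants to Kings or the standard control condition in a 2:1 allocation". On numbers, the Sample Size section says: "The original target sample size was N=60; however, this study ultimately enrolled N=59".

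**The concern.** The baseline survey is completed before the system randomises. Any baseline difference between the arms is therefore chance, and a test of it says nothing about whether the variable predicts the outcome. Prognosis is what makes adjustment useful.

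Used as a route into the model, such a test errs both ways. It admits a variable that differs by luck but is unrelated to the outcome, and it leaves out a prognostic variable whose imbalance falls short of significance. The model also cannot be written down until the arms have been compared.

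The Protocol section gives estimation of intervention effects as the aim of the pilot test. In a trial of 59 people, precision and chance imbalance on the scale outcomes matter even though no power is claimed.

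**Working it through.** The documents state no alpha, effect size or interval width, so there is no figure of theirs to reproduce. The check asks what test-based entry would do at this sample size.

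**Inputs.** N=59 (Sample Size) at 2:1 (Protocol) gives 59 × 2/3 = 39.3 and 59 × 1/3 = 19.7, taken as 39 v 20. This split is derived, not stated. The 2018 Human Subjects Protocol form, item 14, gives 30 per arm, so that split is shown as well. A two-sided alpha of 0.05 is assumed.

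**Imbalance that would be missed.**
- SE of a standardised baseline difference = √(1/39 + 1/20) = 0.275 SD.
- Threshold = t(0.975, 57 df) × SE = 2.002 × 0.275 = 0.551 SD.
- At 30 v 30: SE = √(2/30) = 0.258, threshold 0.517 SD.
- Chance that one covariate shows an imbalance of 0.30 to 0.551 SD, and so goes unflagged: 0.275 − 0.045 = 0.230 (normal approximation). At 30 v 30 the chance of 0.30 to 0.517 SD is 0.245 − 0.045 = 0.20.
- If the covariate correlates 0.5 with the outcome (assumed), an unadjusted imbalance of that size moves the estimate by 0.5 × 0.30 = 0.15 SD to 0.5 × 0.551 = 0.28 SD.

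**Chance flags.** With 5, 8 or 10 independent baseline variables, the chance that at least one is significant is 1 − 0.95^k = 23%, 34% or 40%.

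**Interval width.** Linear models were simulated at 39 v 20 with independent normal covariates and no treatment effect (8,000 runs per setting; 4,000 with eight covariates). Covariates kept only if baseline p<0.05 were compared with the same covariates always included. Mean 95% CI width is in outcome SD units:

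| Covariates | Total R² | Test-selected | Fixed | Fixed set is |
|---|---|---|---|---|
| 3 | 0 | 1.103 | 1.127 | 2% wider |
| 8 | 0 | 1.124 | 1.192 | 6% wider |
| 3 | 0.09 | 1.101 | 1.074 | 2.5% narrower |
| 8 | 0.16 | 1.113 | 1.087 | 2% narrower |
| 1 | 0.25 | 1.091 | 0.956 | 12% narrower |
| 3 | 0.30 | 1.098 | 0.945 | 14% narrower |
| 1 | 0.36 | 1.089 | 0.887 | 19% narrower |
| 8 | 0.40 | 1.107 | 0.918 | 17% narrower |

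**Where the gain comes from.** Suppose three covariates are always in the model, and five non-prognostic ones can enter by test. Dropping those five narrows the interval by only about 1.3%, at every R² from 0 to 0.36. The rest must come from including a strong predictor. For a repeated scale the obvious one is its own baseline value. With baseline-to-follow-up correlation r (equal variances, large sample):
- Width relative to analysing follow-up alone is √(1 − r²). At r = 0.3, 0.5 and 0.7 this is 0.954, 0.866 and 0.714. Simulation against test-selected adjustment gave 4.9%, 13% and 28% narrower. At r = 0.7, R² is 0.49, beyond the range in the table.
- Width relative to a change score is √((1 + r)/2) = 0.806, 0.866 and 0.922, which is 19%, 13% and 8% narrower.

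**Type I error.** With test-selected prognostic covariates (total R² 0.25 to 0.40) the simulated rate is 3.6% to 4.3%, below the nominal 5%. In the run with eight non-prognostic covariates it is 5.7%, but the fixed set gives 5.6% on the same data. The Monte Carlo SE there is √(0.05 × 0.95/4000) = 0.34 percentage points.

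**Binary outcomes.** In logistic models at 39 v 20 with three covariates and control risk 15% to 50%, adjustment made the SE of the log odds ratio about 5% larger for non-prognostic covariates. For strongly prognostic ones it was 15% to 19% larger.

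**The case against.** The strongest reply is that much of the set is not chosen by testing. The sentence on multivariate analysis brings in demographic factors whatever the tests show, and the GEE names education, income and social support. Nor does the SAP say that significance decides entry; it says only that differences will be examined. This stands. A reader might infer that all covariates are picked by baseline p-values, and the documents do not support that. Only the baseline-differences part is open to selection, and the link to the tests is an inference. It is the natural one, because the tests are the only means given for identifying a difference. If something else was meant, the set is unspecified and the same remedy applies.

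The plan also already uses the baseline value of the scales, by comparing the increase from baseline to 6 months. That is fair. The gain over a change score is therefore the relevant one for that comparison, and it shrinks as the correlation rises.

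A reader might further infer that a fixed set always gives tighter intervals at no cost. It does not: with non-prognostic covariates the intervals widen by 2% to 6%. For the binary outcomes adjustment does not narrow the log-odds interval. The conditional odds ratio also moves away from 1, so power need not fall. Self-reported testing has essentially no varying baseline value, since eligibility excludes a test in the prior 6 months.

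Finally, false-positive inflation or a loss of planned power might be suspected. The simulations show no such inflation. The Statistical Power section says that the pilot is not powered, and the SAP calls its efficacy results preliminary.

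**Conclusion.** The point holds for one component of the adjusted models. On the natural reading, the baseline-differences part of the covariate set turns on significance tests between randomised arms. These select on chance imbalance and, at about 39 v 20 with alpha 0.05, pass over imbalances below about 0.55 SD (0.52 SD at 30 v 30).

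The harm is residual imbalance and lost precision on the continuous scales, not invalid inference. Its size depends on prognosis: roughly 2% to 19% in interval width for R² of 0.09 to 0.40 in linear models, mostly through the outcome's own baseline value. The arm sizes, alpha, entry rule, covariate independence and R² values are all assumptions. In an unpowered pilot this should be changed, but it does not undermine the study.

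**What to change.** - Present the baseline table descriptively, without t or chi-square tests between arms.
- Remove baseline differences as a route into the model, and replace the unlisted demographic factors with one short fixed list for all adjusted models: education, income and social support, which the SAP already names for the GEE. Specify pre-randomisation values, because Table 1 of the Human Subjects Protocol form schedules social support after the intervention as well.
- For the five continuous scales (HIV knowledge, PrEP knowledge, internalized homophobia, everyday discrimination, medical mistrust), add the outcome's own baseline value.
- Label any model that adds a variable because it looked imbalanced as a sensitivity analysis.
- Claim no gain in precision for the binary outcomes.

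This costs SAP wording only and needs no new data, since the SAP already relies on baseline values of these scales. The downside is an interval about 2% to 6% wider if the covariates prove unrelated to the outcome, so the list should stay short. If the analysis has already been run, report the fixed-set model and disclose how covariates were chosen.

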**Table 1: Study measures to be collected from participants**

Construct	Measures	# Items	Collection Times
Prescreening	Age, gender, sex, race, orientation, English speaking, sexually active, prior HIV testing 	9	Pre-screening
Contamination	Familiarity with aBSB in social network and components experienced by the participant 	3	Pre, 3-, and 6-
Prevention Knowledge	Subset of HIV Knowledge Questionnaire (HIV-K-Q)  and PrEP knowledge in YMSM 	11	Pre-, post-, and 6-
Culture	Internalized Homophobia Scale Revised (IHP-R)  , Sub-scale, Perceived Racism Scale (PRS),  Sub-scale, Medical Outcomes Study Social Support Survey (MOS) 	29	Pre-, post-, 3- and 6-

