### BSB Intervention Specification and Unique Features

Characteristic	Standard Street Outreach	Brothers Saving Brothers (BSB)
Presentation	Presents as expert providing information and services	Communicates respect for clients as experts on their own behavior and emphasizes personal choice and responsibility
Assessment	Focuses on brief risk assessment	Focuses on assessment of readiness to learn HIV status in addition to brief risk assessment
Education	Focuses on providing standardized HIV education	Focuses on exploring ambivalence about learning HIV status with tailored education as needed
Support for Self-Efficacy	No specific component	Verbally affirms specific strengths to boost confidence for behavior change

Overall Communication	Training involves presenting information in a non-judgmental, respectful manner	Training involves specific client-centered micro-skills and strategies to elicit and reinforce motivational statements
-----------------------	---	--

b. What is the probable length of time required for the entire protocol (i.e., recruitment through data analysis to study closure)? 4 years

c. What is the total amount of time each participant will be involved? Maximum 4 years (staff). If CBO staff are engaged at the onset of the study and are still available at the conclusion, they could be participatory for the full 4-years. Black YMSM who participant in focus groups or in-depth interviews will be engaged for 1 day. Black YMSM who enroll in the effectiveness-implementation study will be active for 6 months.

d. If different phases are involved, what is the duration of each phase in which the participants will be involved? If no phases are involved, enter "None." None

e. List the procedures, the length of time the procedure takes, the total # of times the procedure is performed, and indicate whether each is performed solely for research or would already be performed for treatment or diagnostic purposes (routine care) for the population.  
*-Insert additional table rows as needed.*  
*-If procedure is sometimes research and sometimes routine care, include on separate lines with number of times as each.*

Procedure	Length of Time Required of Participants	Total # of Times the Procedure is Performed	Research (Res) —OR— Routine Care
Focus Group	1 hour	1	 Res  Routine

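### Within-arm change on five scales is listed as a way to examine the intervention's effect, beside the between-arm comparison, and the plan does not say which carries the conclusion

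*Combined protocol and SAP*

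**What the plan says.** The Protocol section gives the purpose of the pilot: "We will pilot-test the adapted intervention to estimate intervention effects". It describes a randomised design: "The system will then randomize participants to Kings or the standard control condition in a 2:1 allocation".

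In the Statistical Analysis Plan, the sentence on the five scales opens "To examine the preliminary effect of the intervention, we compared changes over time" and ends "and medical mistrust within each group, as well as the increase from baseline to 6-month between the two groups". One purpose clause therefore governs two analyses, change within each arm and the between-arm comparison of the increase to 6 months. Neither is called descriptive, supportive or main. The section uses the word descriptive only for the characteristics of the sample.

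The same section plans, in general terms, "multivariate statistics adjusting for demographic factors and baseline differences". It does not say that each scale will be adjusted for its own baseline value. The Statistical Power section states that the pilot is not powered.

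**The concern.** Randomisation protects the comparison between arms. It does not protect the comparison of an arm with its own past. Any effect of Kings on a scale is mixed, within the Kings arm, with whatever else changed over six months and with the effect of answering the same items again.

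For knowledge, the documents make change in both arms plausible. Table 1 of the IRB Human Subjects Protocol (item 14) repeats the knowledge items before the session, after it and at 6 months. The intervention table in item 17 says of standard street outreach: "Focuses on providing standardized HIV education".

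If both arms change by a similar moderate amount, separate tests in each arm will often be significant in one arm only, through chance and arm size. A report that set such p-values side by side could suggest an effect that the randomised contrast does not support.

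**Working it through.** The plan gives no significance level, SD, expected change or within-arm test for these scales, so there is no stated figure to reproduce. The calculation below only illustrates the size of the risk.

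**Inputs from the documents.** The Sample Size section says "this study ultimately enrolled N=59". The Protocol section gives 2:1 allocation, and 59 × 2/3 = 39.3, so I take 39 v 20. Item 14b of the IRB form gives 30 v 30, so I show that too.

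**Assumptions not in the documents.** A paired t test in each arm, two-sided 0.05, the same true change d (in SDs of change) in both arms, equal SDs and no loss. The true between-arm effect is therefore zero.

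**Step 1: power within one arm.** Power(n, d) = P(|T| > t at 0.975 with n − 1 df), where T is noncentral t with n − 1 df and noncentrality d√n. At d = 0.4 this gives 0.682 for n = 39, 0.397 for n = 20 and 0.563 for n = 30.

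**Step 2: significant in one arm only.** The arms are independent, so the probabilities multiply. At d = 0.4:

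- 39 v 20, Kings only: 0.682 × (1 − 0.397) = 0.41.
- 39 v 20, control only: 0.397 × (1 − 0.682) = 0.13.
- 30 v 30, each direction: 0.563 × (1 − 0.563) = 0.25.

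Across the range:

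| True change in both arms (SD) | 39 v 20: Kings only | 39 v 20: control only | 30 v 30: each direction |
|---|---|---|---|
| 0 | 5% | 5% | 5% |
| 0.2 | 20% | 10% | 15% |
| 0.3 | 34% | 14% | 23% |
| 0.4 | 41% | 13% | 25% |
| 0.5 | 37% | 8% | 19% |
| 0.6 | 27% | 3% | 10% |
| 0.8 | 8% | under 1% | 1% |
| 1.0 | 1% | under 0.1% | not computed |

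The value at 0.4 SD is about the peak. With equal arms, each direction is p(1 − p), which cannot exceed 25%, and there is no tilt towards Kings. Under the same assumptions a between-arm test at 0.05 is wrong in 5% of trials, whatever change the arms share.

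**Step 3: precision of the between-arm contrast, 39 v 20.** The unadjusted 95% CI half-width is 2.002 × √(1/39 + 1/20) = 2.002 × 0.275 = 0.55 SD of change.

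**Step 4: gain from adjusting for the scale's own baseline.** Assume equal SDs at baseline and 6 months and correlation r between them. In raw-scale SDs, the change score has SD √(2(1 − r)) and the ANCOVA residual has SD √(1 − r²), so their ratio is √((1 + r)/2).

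| r | Change-score half-width | ANCOVA half-width | Narrower by |
|---|---|---|---|
| 0.3 | 0.652 | 0.526 | 19% |
| 0.5 | 0.551 | 0.477 | 13% |
| 0.7 | 0.427 | 0.393 | 8% |

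**The case against.** The strongest reply is that the safeguard is already there. The sentence that lists within-arm change also plans the between-arm comparison, the section calls the effect preliminary, and the pilot is declared unpowered. All of that stands, and it is why the point is minor. It does not settle which analysis decides the conclusion.

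The documentary support for change in both arms is also limited. It concerns knowledge only. Item 14b calls the Table 1 variables tentative. The item 17 table contrasts outreach with Brothers Saving Brothers, whereas the Statistical Analysis Plan refers to an app. The case against within-arm inference does not depend on these details, because within-arm change is uncontrolled on any scale.

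Some stronger readings are tempting but not supported:

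- **That the plan counts significance in Kings alone as efficacy.** No such rule is stated, so the 41% is not the error rate of anything the plan commits to.
- **That regression to the mean inflates within-arm change.** No eligibility criterion selects participants on any of the five scales.
- **That the between-arm test is a pooled t test that fails under unequal SDs.** Student's t is specified for baseline differences; for efficacy the plan mentions t tests only generically.
- **That the generalized estimating equation either cures or repeats the problem.** Its sentence names no outcome and no arm-by-time term, so it supports neither claim.

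**Conclusion.** The point holds in a limited form, with minor severity. The plan lists an uncontrolled comparison as a way to examine the intervention's effect, on a par with the randomised one, and gives neither priority. A reader might infer that a between-arm analysis is missing; it is not. The consequence is confined to the interpretation of five scales.

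The size of the risk depends on a shared true change that the documents do not give. At 39 v 20 and equal SDs, the misleading pattern in favour of Kings is uncommon at no change or very large change, and ranges from 20% to 41% for changes of 0.2 to 0.6 SD. The tilt towards Kings rests on the 2:1 split and on equal SDs. It disappears at 30 v 30.

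**What to change.** State that within-arm change on the five scales is descriptive, reported as means with 95% CIs and without efficacy inference. State that conclusions on these scales rest on the between-arm difference at 6 months with its 95% CI, from an ANCOVA adjusted for the baseline value of the same scale. The planned increase from baseline already requires those baseline values. General adjustment for baseline differences is not a substitute, since it need not include each scale's own baseline.

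The cost is wording plus one model per scale on data already collected. Within-arm p-values are lost. What remains is imprecise (unadjusted half-width about 0.55 SD of change), as expected in an unpowered pilot. Enrolment is complete and the sentence is in the past tense, so the report should disclose this as a reporting rule set afterwards and should not present it as pre-specified.

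### The between-arm comparison of the five scales uses the change to 6 months without clearly adjusting for each scale's own baseline, which costs precision in a 59-person pilot

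*Combined protocol and SAP*

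**What the plan says.** The SAP (Statistical Analysis Plan section) describes two comparisons for the five scales. One is within arm: "we compared changes over time in HIV knowledge, pre-exposure prophylaxis knowledge, internalized homophobia, everyday discrimination, and medical mistrust within each group". The other is between arms: "as well as the increase from baseline to 6-month between the two groups". The t test is among the bivariate methods it lists for preliminary efficacy.

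Two other sentences in that section concern adjustment:

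- Efficacy will also be assessed with "multivariate statistics adjusting for demographic factors and baseline differences". Earlier, the section says "Baseline differences between the intervention group and control group will be examined using student's t tests", with chi-square tests for categorical variables.
- The effect will be examined further with a "generalized estimating equation controlling for potential confounders including education, income and social support".

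Neither sentence names the baseline value of the scale being analysed. The plan does not say which outcomes the GEE covers, or whether baseline is one of its repeated responses.

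The baseline scores will exist. The Data Collection section lists a survey at "2) pre-randomization, pre-intervention or control data collection". On size, the Protocol section says the system will "randomize participants to Kings or the standard control condition in a 2:1 allocation", and the Sample Size section reports that "this study ultimately enrolled N=59".

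**The concern.** Comparing change scores amounts to subtracting the whole of the baseline score, that is, fixing its coefficient at 1. With equal SDs the best coefficient is the baseline-to-6-month correlation, which is below 1, so subtraction over-corrects and adds noise. ANCOVA estimates the coefficient from the data.

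The sentence on adjusting for baseline differences most naturally means variables on which the arms are found to differ in the baseline tests, though the text does not settle this. On that reading a scale's own baseline would enter its model only after a chance imbalance. Its value as a covariate comes from how well it predicts the 6-month score, not from whether the arms happen to differ on it.

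The Protocol section gives estimating intervention effects as the purpose of the pilot, and about 20 people are in the control arm. The width of the interval therefore decides how much these scales can tell anyone planning a later trial.

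**Working it through.** The plan states no power, SD, effect size or interval width, so there is no figure of its own to reproduce. The check compares the two methods over a range of assumed correlations.

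**Inputs.** N = 59 (Sample Size) and 2:1 allocation (Protocol), taken as 39 v 20. Assumed: correlation rho between baseline and 6-month score; equal SDs at first; no missing data at first.

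**Variance ratio.** With equal SDs, the variance of the arm difference is proportional to 2(1 − rho) for the change score and to 1 − rho² for ANCOVA. The ratio ANCOVA/change is (1 − rho²) / [2(1 − rho)] = (1 + rho)/2. At rho 0.5 this is 0.75: variance 25% lower, and SE lower by 1 − √0.75 = 13%.

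**Half-width of the 95% CI, in SD units.** √(1/39 + 1/20) = 0.275.

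- Change score: t(57) × √[2(1 − rho)] × 0.275
- ANCOVA: t(56) × √[(1 − rho²)(1 + 1/55)] × 0.275, where 1 + 1/(N − 4) is the expected cost of estimating the slope

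Both t values are 2.00. At rho 0.5: 2.00 × 1.000 × 0.275 = 0.55, against 2.00 × √(0.75 × 1.018) × 0.275 = 0.48.

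| rho | Variance reduction | Half-width, change | Half-width, ANCOVA | Narrower by |
|---|---|---|---|---|
| 0.1 | 45% | 0.74 | 0.55 | 25% |
| 0.3 | 35% | 0.65 | 0.53 | 19% |
| 0.5 | 25% | 0.55 | 0.48 | 13% |
| 0.7 | 15% | 0.43 | 0.40 | 7% |
| 0.9 | 5% | 0.25 | 0.24 | 2% |

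**Simulation.** With 20,000 simulated trials per rho (normal data, 39 v 20), the mean interval was 18.7%, 12.6% and 6.9% narrower at rho 0.3, 0.5 and 0.7. A separate run of 10,000 per rho with no true effect gave bias below 0.005 SD and coverage of 95.0% to 95.4% for both methods.

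**Sensitivity.**

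- *Allocation.* Section 14b of the Human Subjects Protocol form gives 30 v 30 instead of 2:1. The percentages are essentially unchanged, because the allocation term cancels from the ratio.
- *Attrition.* With 20% lost (31 v 16, assumed), the intervals are 18%, 12% and 7% narrower at rho 0.3, 0.5 and 0.7.
- *Unequal SDs.* With k = 6-month SD / baseline SD, the variance ratio is k²(1 − rho²) / (1 + k² − 2·rho·k). Over rho 0.3 to 0.7, after the small-sample cost, the narrowing is about 28% to 20% at k = 0.8 and about 11% to 0% at k = 1.25.

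**Selection by baseline test.** If a difference means p < 0.05 (assumed; no threshold is given), the arms must differ by more than 2.00 × 0.275 = 0.55 SD before a scale's baseline enters. That happens in about 1 in 20 randomised comparisons.

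**Smaller imbalances.** A baseline gap of one SE (0.275 SD) would not trigger that rule. At rho 0.5 it still moves the change-score difference by (1 − 0.5) × 0.275 = 0.14 SD.

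**The case against.** The strongest reply is that the plan may already do this. It names the increase as the quantity of interest but never says that the comparison is unadjusted, and the preceding sentence promises a multivariate analysis as well. Regressing the change on arm plus baseline gives exactly the same arm effect as regressing the 6-month score on arm plus baseline. If the multivariate model includes the scale's baseline, the gain is zero. This stands to the extent that the percentages above apply only against the unadjusted change score, and none is claimed against the multivariate model or the GEE. It does not show that baseline is adjusted for. The wording points to covariates chosen by observed imbalance, and the GEE list, though open-ended, does not name the baseline score. If baseline is a repeated response in the GEE with free arm means, the arm-by-time contrast is essentially the change-score contrast again.

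Second, the range is assumed. That is so, and the gain can disappear: at k = 1.25 and rho 0.8 the variance ratio is exactly 1, and ANCOVA is then about 1% wider through its extra parameter. That is the size of the possible loss, against gains of 7% to 28% in the more favourable cases.

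Third, this is an unpowered pilot whose abstract stresses acceptability and feasibility. The testing and PrEP outcomes are compared by chi-square and Fisher tests, which this point does not touch, and the intervals stay wide either way. All true, and it limits the importance of the point. But the plan does set out to estimate effects on these scales, and the extra precision is almost free.

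Fourth, a change made after outcomes are seen loses the benefit of prespecification. That also stands, and the fix allows for it.

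**Conclusion.** The concern holds, as a matter of efficiency. The planned comparison is unbiased and its intervals have nominal coverage, but the plan does not clearly use the baseline score as a covariate, and the change score it specifies is generally the less precise choice. With equal SDs and rho between 0.3 and 0.7, the 95% CI would be about 19% to 7% narrower under ANCOVA. In large-sample terms, the change score would need 59 × 2/(1 + rho), or about 91, 79 or 69 participants at rho 0.3, 0.5 or 0.7, to match ANCOVA with 59. These figures rest on assumed correlations and SDs, and on comparison with the unadjusted change score alone. The change should be made, but nothing in the planned analysis is invalid without it.

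**What to change.** - For each of the five scales, make the between-arm analysis an ANCOVA of the 6-month score on arm and the participant's own baseline score, included whether or not the arms differ at baseline. Report the adjusted mean difference with its 95% CI.
- State which outcomes the GEE covers. Where it models follow-up scores of these scales, include the baseline value as a covariate; if baseline is one of the repeated responses, say so.
- Keep the raw change by arm as a descriptive summary.

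The cost is SAP wording, one model term in SAS and one degree of freedom per model. It needs no extra data, visits or participants. Because the document already reports final enrolment and describes the scale comparison in the past tense, the analysts should record whether outcome data had been seen. If they had, declare the ANCOVA as a later change and show the change-score result beside it.
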